7.2.2 Visit 1: Enrolment/ Screening /Baseline

The subjects will complete Visit 1 after exiting the MIST-401 Part 2 study. This may be on a different day from the MIST-401-Part 2 study exit, however they should only wear spectacles in between exiting the MIST-401-Part 2 study and entering this study. If this is more than 1-week from the MIST-401-Part 2 study exit then all assessments in the table below will need to be repeated.

Prior to being evaluated, the subject and his/her parent/guardian (if applicable) must have the study explained to them; read or have the informed assent and consent documents read to them and indicate understanding of the documents.

The consent and assent documents will be provided to subjects and their parent/guardians as applicable. The content of the consent and assent documents may vary slightly from country to country, based on the requirements of the respective IRB/IEC. The investigator must ensure that they use only the consent form which has been approved by both the sponsor and the IRB/IEC/Health Authority (if appropriate).

The investigator or designee will explain the study purpose, procedures, and subject responsibilities to the potential subject and his/her parent/guardian (if applicable). The subject's willingness and ability to fulfil the study's requirements will be determined.

If the subject agrees to participate in the study, written informed consent will be obtained from the subject and/or parent or guardian (if applicable). Where the subject is under the country's age where they are able to sign the consent form themselves, written informed assent will be obtained from the subject. The assent and consent forms will be signed and dated in the presence of the investigator's staff after opportunity has been given for discussion, questions or concerns by the subject and his or her parent/guardian (if applicable).

The investigator and the person who explained the informed consent and assent (if applicable) must also sign the documents. The original documents will be retained in the subject's records, and copies will be provided to the subject and parent/guardian (if applicable).

A subject is considered enrolled when the Statement of Informed Consent / Assent documents (where applicable) have been fully executed. The subject will then be added to the enrolment log.

All subjects enrolled should be accounted for, even if they are not dispensed lenses. After enrolment, a subject is considered active and should be accounted for at every visit until the completion of, or discontinuation from the study.

Some baseline data for MIST-402 may include measurements already collected at the final visit for MIST-401 Part 2 (see table below). These measurements do not need to be repeated and the information can be taken from that final visit CRF as long as within a week from enrollment in MIST-402.

The following Screening/Baseline procedures will be conducted on all subjects once enrolled i.e. after the consent/assent (where applicable) documents have been fully executed:

Number	Assessment	Procedure	Instructions and gradings
1	Subject Demographics	Record age, sex and ethnicity	

Number	Assessment	Procedure	Instructions and gradings
2	Medical History	Record medications and associated medical history (such as allergies etc)	
3	Previous Study Lens Wearing Time*	Record the typical insertion & removal times, number of hours worn today, number of days worn per week.	Appendix A – Subjective Assessments
4			
5			
6	Entrance Distance VA	Record the Monocular high contrast distance VA with habitual correction	Appendix A - Visual Acuity and Refraction
7			
8			
10	Manifest Subjective Refraction*	Record the subject's manifest refraction, recording all cylinder in the minus cylinder convention.	Appendix A - Visual Acuity and Refraction
11	BCDVA*	With the manifest refraction record the best corrected distance VA	Appendix A - Visual Acuity and Refraction
12			
13			

Number	Assessment	Procedure	Instructions and gradings
14	Cycloplegia (only if not taking the information from MIST-401 study)	Induce Cycloplegia according to the instructions provided and wait for 25 minutes before conducting cycloplegic assessments.	Appendix A - Cycloplegia
15			
16	Cycloplegic Auto Refraction*	For the auto-refraction measurements the average of the 5 measurements should be recorded on the eCRF after eliminating sphere or cylinder readings that are more than 1.00D from the mode.	Appendix A - Visual Acuity and Refraction
17	Axial Length*	For the axial length measurements, the average of the 5 measurements should be recorded on the eCRF.	Appendix A - Ocular Characteristics
18			
19			
20	Eligibility	Confirm if subject is eligible and complete the eligibility criteria checklist. If at this point the subject is found to be ineligible, then complete an Exit eCRF and exit the subject from the study. The Investigator will also update the Enrolment Log and complete the Source Document Record – see Section 11.5 for further details	

* If already collected for the MIST-401 Part 2 study final visit, this measurement does not need to be repeated and the information can be taken from the final visit CRF as long as within a week of enrolment in MIST-402.

7.2.3 Visit 1: Trial Fit and Dispensing

If eligible, the subjects will undergo a trial fit in each eye with the lenses.

Number	Assessment	Procedure	Instructions and gradings
1	Lens Parameters	Record the parameters of the lenses (lot number, lens powers). Lens type will be decided according to the randomisation log. Lens power will be based on non- cycloplegic subjective distance refraction	Appendix A – Lens Fit Assessment
2	Settling Time	Allow the lenses to settle for at least 10 minutes	
3			
4	DVA with CLs	With the contact lenses in record the best corrected distance VA	Appendix A - Visual Acuity and Refraction
5	Spherical Over Refraction	With the contact lenses in record the spherical over refraction	Appendix A - Visual Acuity and Refraction
6	DVA with Over Refraction and CLs	With the contact lenses in and spherical over refraction record the best corrected distance VA	Appendix A - Visual Acuity and Refraction
7	Suitability Review	If the subject was not able to achieve at least +0.10 logMAR, a second trial fit is allowed. Repeat procedures 1-8	
8			
9			
10			
11	Dispensing Criteria	Lens fit and vision was acceptable	

The following Trial Fit / Dispensing procedures will be conducted on eligible subjects:

Number	Assessment	Procedure	Instructions and gradings
13	Instructions	 The Participant Instruction Guide will be provided to all subjects and will give instructions regarding lens wear and care. The Investigator or a clinical assistant will review instructions and warnings for lens wear, when to remove lenses, and other important issues with the participant. Participants who appear unable or unwilling to follow instructions to a degree that, in the Investigator's opinion, jeopardizes the participant's wellbeing or the validity of the study, will be discontinued. Subject should be given enough lenses to last until the next visit. Subject will be instructed to wear the lenses for at least 6 days per week and at least 10 hours per day 	

7.2.4 Visit 2: 2-week Follow-Up (optional)

The 2-week follow-up visit will be scheduled 14 days (9-19 days) from the initial lens dispensing date.

This is an optional visit if, in the investigators opinion, it is needed to confirm adaptation to the new lenses. If the 2-week visit is being completed then the subject should wear the study lenses to the appointment.

Number	Assessment	Procedure	Instructions and gradings
1	Concomitant Medications and Medical History Review	Record any changes to concomitant medications or medical history and confirm if the changes are Adverse events	
2			
3			
4			

The following clinical test variables will be recorded on the Follow-Up Visit eCRF:

Number	Assessment	Procedure	Instructions and gradings
5	Entrance Distance VA	Record the Monocular high contrast distance VA with study contact lenses	Appendix A - Visual Acuity and Refraction
6			
7	Spherical Over refraction	With the contact lenses in record the spherical over refraction	Appendix A - Visual Acuity and Refraction
8	DVA with CLs and Over refraction	With the contact lenses in and spherical over refraction record the best corrected distance VA	Appendix A - Visual Acuity and Refraction
9			
10			
11			
12			
13			
14			
15	Instructions	 Subject should be given enough lenses to last until the next visit. Subject will be instructed to wear the lenses for at least 6 days per week and at least 10 hours per day 	

7.2.5 Visit 3: 6-month Follow-Up

The 6-month follow-up visit will be scheduled 6-months (166-194 days) from Visit 1. The subject should wear the study lenses to the appointment.

The following clinical test variables will be recorded on the Follow-Up Visit eCRF:

Number	Assessment	Procedure	Instructions and gradings
1	Concomitant Medications and Medical History Review	Record any changes to concomitant medications or medical history and confirm if the changes are Adverse events	
2			
3			
4			
5			
6	Entrance Distance VA	Record the Monocular high contrast distance VA with study contact lenses	Appendix A - Visual Acuity and Refraction
7			
8	Spherical Over Refraction	With the contact lenses in record the spherical over refraction	Appendix A - Visual Acuity and Refraction
9	DVA with CLs and Over Refraction	With the contact lenses in and spherical over refraction record the best corrected distance VA	Appendix A - Visual Acuity and Refraction
10			
11			
12			
13			

Number	Assessment	Procedure	Instructions and gradings
14			
15	Cycloplegia	Induce Cycloplegia according to the instructions provided and wait for 25 minutes before conducting cycloplegic assessments.	Appendix A – Cycloplegia
16			
17	Cycloplegic Auto Refraction	For the auto-refraction measurements the average of the 5 measurements should be recorded on the eCRF after eliminating sphere or cylinder readings that are more than 1.00D from the mode.	Appendix A - Visual Acuity and Refraction
18	Axial Length	For the axial length measurements, the average of the 5 measurements should be recorded on the eCRF.	Appendix A - Ocular Characteristics
19			
20	Instructions	 Subject should be given enough lenses to last until the next visit. Subject will be instructed to wear the lenses for at least 6 days per week and at least 10 hours per day 	

7.2.6 Visit 4: 12-month Follow-Up

The 12-month follow-up visit will be scheduled 12-months (316-404 days) from Visit 1. The subject should wear the study lenses to the appointment.

Number	Assessment	Procedure	Instructions and gradings
1	Concomitant Medications and Medical History Review	Record any changes to concomitant medications or medical history and confirm if the changes are Adverse events	
2			
3			
4			
5			
6			
7	Entrance Distance VA	Record the Monocular high contrast distance VA with study contact lenses	Appendix A - Visual Acuity and Refraction
8			
9	Spherical Over Refraction	With the contact lenses in record the spherical over refraction	Appendix A - Visual Acuity and Refraction
10	DVA with CLs and Over Refraction	With the contact lenses in and spherical over refraction record the best corrected distance VA	Appendix A - Visual Acuity and Refraction
11			
12			
13			
14			

The following clinical test variables will be recorded on the Follow-Up Visit eCRF:

Number	Assessment	Procedure	Instructions and gradings
15			
16			
17			
18			
19			
20	Cycloplegia	Induce Cycloplegia according to the instructions provided and wait for 25 minutes before conducting cycloplegic assessments.	Appendix A – Cycloplegia
21			
22	Cycloplegic Auto Refraction	For the auto-refraction measurements the average of the 5 measurements should be recorded on the eCRF after eliminating sphere or cylinder readings that are more than 1.00D from the mode.	Appendix A - Visual Acuity and Refraction
23	Axial Length	For the axial length measurements, the average of the 5 measurements should be recorded on the eCRF.	Appendix A - Ocular Characteristics
24			

Number	Assessment	Procedure	Instructions and gradings
25			
26	Instructions	 Subject should be given enough lenses to last until the next visit. Subject will be instructed to wear the lenses for at least 6 days per week and at least 10 hours per day All unused study lenses will be collected from any subjects that were randomised to the Proclear 1- day contact lenses and retained at site until the Close out visit, unless otherwise instructed by VCR or the Sponsor 	

7.2.7 Study Exit

The Study Exit eCRF must be completed when a subject exits the study. This will occur either at study completion, i.e. after Visit 4, or if the subject is discontinued from the study at another time. A Study Exit eCRF must be completed for all subjects who have a fully executed consent form. The exit date should also be recorded on the subjects named patient notes i.e. the Source Document Record. Post-study follow-up visits will be scheduled if the Investigator judges this is necessary. In this case the Exit eCRF will not be completed until all post-study visits have been completed.

At the study Exit Visit the following measurements are taken and recorded on the Exit eCRF:

Number	Assessment	Procedure	Instructions and gradings
1	Manifest Subjective Refraction	Record the subject's manifest refraction, recording all cylinder in the minus cylinder convention.	Appendix A - Visual Acuity and Refraction
2	BCDVA	If the VA at the Exit Visit is two or more lines worse than at Baseline, the Investigator will be required to provide an explanation and complete an adverse event eCRF	Appendix A - Visual Acuity and Refraction
3			
4	Subject Study Exit	Record if the subject has successfully completed the study. If the subject is being exited due to discontinuation, further details need to be recorded on the exit form. This is described in Section 7.4.	

7.3 Clinical Variables

Table 2 summarises the clinical measurements to be taken at each visit.

The Baseline visit for MIST-402 is expected to be on the same day as MIST-401 Part 2 Exit Visit and will take place straight after the visit.

The MIST-402 Exit Visit will ordinarily take place immediately following Visit 4, but may take place earlier if a subject discontinues from the study. Slit lamp assessment to be performed if Exit Visit does not take place immediately after a follow-up visit.

	BASELINE	DISPENSE		FOLLOW UP VISITS			
PROCEDURES		Day 0	2 wk	6 Mo	12 Mo	UN- SCHED	Exit
Informed Consent and Assent	x						
Demographics	X						
Med History	X						
	X *		X	x	x		
Concomitant medications review	x		X	x	x	x	
Lensometry	X*				X		
Entrance VA	X		Х	X	X	X	
		X	Х	X	X		
	Х*						
	X*				X		Х+
	X*				х		Х+
)	x				х		
	X		X	X	X	X	
)		x	х	X	X		
Contact lens over-refraction		X	Х	X	X		
		X	X	X	X		
	X*			X	X		
Cycloplegic auto-refraction	X*			X	X		
Cycloplegic biometry (axial length)	Х*			x	x		
	X*				X		
				X	X		
Exit VA			Х	X	X		Х+
Dispense study lenses		X	Х	X			
Complications, Adverse Events &device malfunctions		Corr	plete wh	ere applic	able		
Parent/Guardian Informed Consent (if applicable)	x						
	X						

 Table 2:
 Summary of Clinical Measurements

* If already collected for the MIST-401 Part 2 study final visit, this measurement does not need to be repeated and the information can be taken from that final visit CRF as long as within a week of enrolment in MIST-402. + if not completed at the associated visit.

7.4 Subject Discontinuation

Subjects may be discontinued from the study in the event of any of the following occurring:

i. Unacceptable subjective discomfort (i.e. lens cannot be tolerated or worn)

- ii. Unacceptable slit lamp findings
- iii. Unacceptable fit (i.e. lens too tight or too loose)
- iv. At the discretion of the Investigator or the subject
- v. Subject out of Rx range for the lenses.

In the event of discontinuation, the Study Exit eCRF must be completed and the study exit date recorded on the Source Document Record. The Investigator will indicate the primary reason for discontinuation by selecting one of the boxes provided on the Exit eCRF. Comments can be added to the eCRF if necessary.

If a subject is discontinued outside of a visit window, an Unscheduled Visit eCRF must also be completed

7.5 Unscheduled Visits

An unscheduled visit is defined as any follow-up that occurs outside the visit window of the scheduled visit. A visit is also classified as unscheduled if the subject is seen a second time within the scheduled visit window.

Investigators should try as far as possible to schedule follow-up visits within the window. If this is not possible, and the visit falls outside the window, the visit will be an unscheduled visit, unless it has been agreed with VCR that it can be considered a scheduled visit.

Alternatively, the Investigator might judge that a follow-up visit is in the best interest of the subject and schedule two visits within the same window, e.g. follow-up of an adverse event. Unscheduled visits are also made available anytime at the subject's request.

Unscheduled visits will be recorded on the Unscheduled Visit eCRF. All variables listed on the forms must be completed unless the subject exhibits a condition that prohibits the completion of a full visit. If this is the case, a written explanation is required in the comments section (e.g. not wearing lenses due to discomfort).

Presenting VA and slit lamp variables must always be completed and the reason for the visit and any actions taken must be indicated on the forms.

7.6 Site Training and Visits

The study initiation will take place via on-line training modules and a phone call.

The sponsor or VCR may choose to initiate a site visit as deemed appropriate. If this occurs, VCR will email prior to the visit to arrange a convenient time. Interim and close-out monitoring visits will be documented in the Monitoring Plan which is a separate document.

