5 MATERIALS

5.1 Study Lenses

Table 1:Lens Details

Brand	Proclear 1 Day
Manufacturer	CooperVision
Material/ water content	omafilcon A / 62%
Design	Single vision
Base curve (mm)	8.70
Diameter (mm)	14.2
Sphere powers (D)	-0.25D to -8.00D (0.50D steps after - 6.00D)

Only lenses distributed by VCR may be used for the study.

If additional lenses are required, investigators should contact VCR.

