7.2 Study Visits

7.2.1 Visit Schedule

There will be a maximum of four scheduled visits as follows:

- Visit 1: Baseline / Trial Fit / Lens Dispensing
- Visit 2: 2-week Follow Up (Optional)* (14 days ± 5 days from dispensing)
- Visit 3: 6-month Follow Up (180 days ± 14 days from dispensing)
- Visit 4: 12-month Follow Up and Exit (360 days ± 44 days from Dispensing)

* This is an optional visit if, in the investigator's opinion, it is needed to confirm adaptation to the new lenses

A Visit Schedule will be supplied to all sites and will list the visit windows; this can assist in the scheduling of visits within the appropriate window.

The Investigator should confirm with the subject that they are able to attend the follow-up visit within the visit window before enrolling them in the study. If, in extreme situations (sickness, unforeseen circumstances), the subject can only attend outside the visit window, the Investigator should discuss with VCR whether this visit can be considered a scheduled visit.

A scheduled follow-up visit may only take place when the subject attends wearing the study lenses. If this is not the case and the subject is not experiencing any problems with the lenses, the appointment will be re-scheduled, ideally within the visit window.

See Section 7.5 for instructions regarding unscheduled visits.

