10.3 Statistical Considerations

All statistical analyses will be performed using the SAS software Version 9.4 or later (SAS Institute, Cary, NC). All data summaries will be performed using Microsoft Excel 2013 or later.

The final analysis will be completed after all subjects have been exited from the study, all queries have been resolved, and the database has been locked.

The mean annual myopic progression will be calculated by dividing the myopic progression for the years in question by the number of years for each subject.

The overall type I error rate will be preserved at 5%. The co-primary hypotheses will be simultaneously evaluated using α =0.05.

Data from unscheduled visits will not be included in the analysis.

10.4 Analysis Population

The statistical analysis for efficacy hypothesis testing will be performed as follows:

- 1. All available data this will include all data from subjects that have completed followup visits. Counts of missing data will be included in the summary statistics.
- 2. Intent-to-treat this will include any subject that has completed at least the 6-month visit. Missing data for 12-month myopia progression and axial length will be extrapolated, where possible, from the 6-month data for the intent-to-treat analysis.

10.5 Descriptive Statistics

Descriptive statistics will be reported at dispensing and each follow-up visit. Continuous variables will be summarized using mean, standard deviation, and range; and categorical data variables will be summarized using percent frequency distribution, mean, and SD. Nominal variables will be summarized using percentages.

Summaries will be presented by group (T3: 3 years of MiSight wear and T6: 6 years of MiSight wear.

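### The exit, visit and data-exclusion rules can leave 12-month SERE and axial length missing for subjects who stop study lenses, and for out-of-range exits the loss leans towards non-inferiority

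*Combined protocol and SAP*

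**What the plan says.** Four provisions of the combined protocol and SAP meet here.

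- **Section 7.4, Subject Discontinuation.** Subjects may be discontinued from the study for several reasons, one being "Subject out of Rx range for the lenses". Lens powers end at -8.00 D (section 5.1), and the eligibility criteria in 4.4 and 4.5 set no refractive limit short of that. The section adds: "If a subject is discontinued outside of a visit window, an Unscheduled Visit eCRF must also be completed".
- **Section 7.2.1, Visit Schedule.** "A scheduled follow-up visit may only take place when the subject attends wearing the study lenses". A subject who comes without lenses but has no lens problem is re-booked: "the appointment will be re-scheduled, ideally within the visit window".
- **Table 2 and section 7.2.7.** The rows for "Cycloplegic auto-refraction" and for axial length are marked at baseline, 6 and 12 months, not in the Unscheduled or Exit columns. The refraction listed for the exit visit is manifest, not the cycloplegic endpoint.
- **Section 10.3.** "Data from unscheduled visits will not be included in the analysis".

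Section 10.4 defines two analysis sets. One uses all available data. The intent-to-treat set needs a completed 6-month visit and extrapolates a missing 12-month value from it where possible. No extrapolation method is given, and neither set is named as primary.

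**The concern.** Moving beyond the lens range during the year is myopic progression, and myopic progression is the primary outcome. A subject who leaves for this reason between visit windows has no later scheduled visit, has neither primary measurement listed at exit, and has any unscheduled data set aside. Lens wear is not needed for either measurement: autorefraction is done under cycloplegia, and Appendix A has contact lenses off for axial length.

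The primary claim is that post-cessation progression is not worse than the control rate by more than 0.25 D or 0.1 mm. Losing faster progressors lowers the observed post-cessation mean, which makes that claim easier to reach. The study is open label, and whether an out-of-window visit counts as scheduled is agreed case by case with the CRO (7.2.1, 7.5). It is therefore better to settle the handling in advance.

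**Working it through.** **1. The plan's power figures (section 10.1).** Inputs: n = 46 (T3, paired) and 44 (T6, against 46); SDs 0.36 D, 0.20 D, 0.10 mm, 0.10 mm; margins 0.25 D and 0.1 mm; one-sided 5%; expected difference 0. Power = Φ(margin/SE − 1.645).

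| Comparison | SE | Power found | Plan |
|---|---|---|---|
| SERE T3 | 0.36/√46 = 0.053 | 0.999 | 100% |
| SERE T6 | 0.20·√(1/44 + 1/46) = 0.042 | >0.999 | 100% |
| AL T3 | 0.10/√46 = 0.015 | 1.000 | 100% |
| AL T6 | 0.10·√(1/44 + 1/46) = 0.021 | 0.999 | 99% |

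The figures reproduce. With 20% random loss (37 and 35 subjects), power is still 0.994 (SERE T3) and 0.997 (AL T6). Lost numbers are not the problem; selective loss would be.

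**2. What each exit time leaves.**

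| Exit | All available data | Intent-to-treat |
|---|---|---|
| Before the 6-month visit | no primary outcome | subject excluded |
| At an in-window 6-month visit | 6-month value only | 12-month value extrapolated |
| Between 6 and 12 months | 6-month value only | 12-month value extrapolated |
| At an in-window 12-month visit | observed | observed |

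**3. Upper bound.** Suppose exactly the fastest k of n are lost, rates are normal, and no 6-month value helps. With p = k/n and c the (1−p) normal quantile, the mean is understated by SD·φ(c)/(1−p).

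- SERE T3, k = 5: 0.36 × 0.209 = 0.075 D (30% of the margin); k = 2: 0.035 D (14%).
- SERE T6, k = 5: 0.20 × 0.217 = 0.043 D (17%); k = 2: 0.020 D (8%).
- AL, k = 5: 0.021 mm (T3) and 0.022 mm (T6), or 21–22%.

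With the true difference at the margin, false non-inferiority would rise from 0.05 to 0.17 (T3) or 0.13 (T6) with two lost, and to 0.48 or 0.29 with five lost. The understatement scales with the SD, so a larger one-year SD would raise it in proportion.

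**4. Loss through crossing -8.00 D.** The documents give no baseline SERE distribution, progression rates or dropout, so these are assumptions. Baseline is normal, restricted to the lens range. Annual progression is 0.4 D (SD 0.20 or 0.36) or 0.6 D (SD 0.36). The 6-month change is half the annual change plus noise of SD 0.15 D.

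| Baseline mean (SD), D | Eyes crossing | Understated, all crossers lost | Understated, only 6-month crossers lost | Overstated, 6-month change doubled |
|---|---|---|---|---|
| -3.5 (1.25) | 0.05–0.12% | 0.0001–0.0004 D | ≤0.0001 D | ≤0.0001 D |
| -4.0 (1.50) | 0.5–1.0% | 0.0006–0.0030 D | ≤0.0009 D | ≤0.0006 D |
| -5.0 (1.75) | 2.9–5.0% | 0.0031–0.0123 D | ≤0.0045 D | ≤0.0031 D |

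The largest understatement, 0.0123 D, is 0.0123/0.25 = 5% of the margin. Crossers there are only 0.0123/0.0495 = 0.25 D/year faster than the rest, because crossing depends mainly on starting level. Exit is by subject, not by eye. If the two eyes were unrelated, the fraction lost would about double, but half the lost eyes would be non-crossers, so the understatement would barely change.

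**The case against.** The strongest reply is that the plan already contains most of the loss. Discontinuation is permissive. A subject found out of range at an in-window 6- or 12-month visit has both measurements listed at that visit. Anyone with a 6-month visit stays in the intent-to-treat set, and doubling a fast early change errs slightly the other way. Section 5.4 keeps subjects who wear lenses too little. The Exit eCRF records the reason for leaving, and missing data are counted. In T3, losing a pair also removes that subject's Part 1 rate, which may partly offset the bias; T6 has no such offset. All of this stands. It leaves exits before 6 months, and it leaves later exits resting on an extrapolation with no stated method.

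Three stronger readings are tempting and not supported:

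- A reader might infer that the rules remove the fastest progressors' outcome outright and that neither analysis set helps. The intent-to-treat extrapolation contradicts this for anyone seen at 6 months.
- A reader might infer that every stop of lens wear biases towards non-inferiority. Discomfort, fit, slit lamp findings or personal choice need not track progression, and the documents give no data on it.
- A reader might suppose 10% lost at 1.0 D/year faster than the rest, hence 0.10 × 1.0 = 0.10 D. That mixture alone has SD √(0.1 × 0.9) × 1.0 = 0.30 D, above the planned T6 SD of 0.20 D.

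There is also a fair warning about any remedy. Annualising a change over 2 to 3 months multiplies its measurement error by 12/3 = 4 to 12/2 = 6. A subject off study lenses may use a correction that itself affects progression.

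**Conclusion.** The point holds in a limited form. The rules can leave the 12-month primary outcomes missing: completely before the 6-month visit, and replaced only by extrapolation after it. For out-of-range exits the missingness depends partly on progression, so an analysis of observed 12-month values leans towards non-inferiority. No sensitivity analysis beyond the extrapolation is specified. The size is unknown and probably small. The simulated figure rests on assumed baselines and applies the -8.00 D limit to SERE, although section 7.2.3 sets lens power from non-cycloplegic refraction. The larger bound needs exactly the fastest subjects to be lost. This does not threaten the design; it is an improvement worth making because it is cheap.

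**What to change.** Leave the rules on stopping study lenses as they are, but separate them from leaving follow-up.

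- **7.4:** invite subjects who stop study lenses to the already scheduled 6- and 12-month cycloplegic autorefraction and axial length.
- **7.2.1:** exempt these two measurements from the lens-wear condition.
- **10.4:** use the in-window values in the intent-to-treat analysis in place of extrapolation.
- **Table 2, 7.2.7 and 10.3:** if a subject will not return, take both measurements at exit and use them, with actual elapsed time, in a sensitivity analysis only.
- **Reporting:** record the correction worn after stopping, and report discontinuations by reason and group.

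The cost is a short amendment. The 6- and 12-month measurements are already scheduled; the exit ones are extra, for few subjects. The downside is that a few subjects contribute time off study lenses, so the results should also be shown without them.
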